The modern treatment options for distal femur fractures consist of lateral locking plates and retrograde nailing.¹¹ The operative treatment aims to restore the articular surface and maintain the limb alignment and length with stable fixation.^{12,13} The operative treatment can be challenging due to osteoporotic bone and pre-existing implants in knee and hip, possibly limiting the treatment options. A constrained knee prosthesis is an option in very distal and severely comminuted fractures or fractures with a loose knee prosthesis.^{11,13} The non-surgical treatment with a cast leads generally to unsatisfactory results but it is an relevant option for patients with unacceptably high surgical risks.¹³

One of the most common and disabling complication following distal femur fracture is nonunion, leading to demanding reoperations and delayed healing. Distal femur fractures treated with a locking plate are associated with decreased and asymmetric callus formation.¹⁴ The exact incidence of nonunion varies in the literature. However, diverse studies document high nonunion rates (10–22%) with modern lateral locking plates.^{15–23} A recent meta-analysis reported a nonunion rate of only 6% in distal femur fractures treated with a lateral locking plate.²⁴ Distal femur fracture nonunion can lead to mechanical failure of the plate.^{25,26} In a literature review, 75% of implant failures occurred three months after operation due to plate fatigue secondary to delayed union and continuous movement of the fracture site.²⁶

Risk factors for non-union

Distal femur fracture nonunion has a multifactorial background involving different patient-, injury- and treatment-related risk factors. The patient- and injury-related risk factors for non-union described in the literature include obesity^{23,27}, diabetes¹⁵, infection^{6,23,27}, smoking¹⁹ and open fracture^{15,18,23,25,27}. A predictive algorithm in the study by Rodriguez et al showed that with these four risk factors—obesity, infection, titanium plate instead of stainless steel plate, and open fracture—the risk for nonunion was 96% and the absence of these factors reduced the risk to 4%.²³

Fracture comminution has been identified as a risk factor for distal femur fracture nonunion in two studies.^{17,21} However, one study found no correlation between the length of comminution and nonunion.²⁵ Lateral locking plate constructs may not have adequate stability in fractures with severe medial comminution. In comminuted fractures the medial fracture gap above 5mm may increase the risk for fracture nonunion.¹⁹ A retrospective study showed 9,3% plate failures after lateral locked plating of distal femur fractures, and plate failures occurred

average 186 days (range 85-400 days) after operation reflecting the probability of nonunion in these fractures. Open fractures, medial metaphyseal comminution and higher length of the comminution were associated with plate failures.²²

Knee prostheses in periprosthetic distal femur fractures may limit the fracture treatment options, complicate the operation and affect the fracture healing. There was no significant differences between periprosthetic and non-periprosthetic fractures regarding the union-rates (83,8% vs. 78,9%) in a retrospective study.²¹ One study showed periprosthetic fractures to be associated more often with failed hardware than non-periprosthetic fractures.²⁵ A recent national database study with a large cohort of patients indicates no differences in mortality, reoperation and major complications between periprosthetic and native distal femur fractures.²⁸ Patients with periprosthetic fracture had a higher rate of wound complications.²⁸

Distal femur fracture nonunion rate might be lower in elderly patients with low-energy injuries. A recent study from Sweden showed only 4% nonunion in a geriatric study population with a median age of 79.²⁹ In their study, no patients over 80 years underwent surgical intervention for nonunion. Patients with nonunion were younger and had open fractures more commonly, reflecting the higher trauma energy.²⁹ On the other hand, another study with a geriatric study population (average age 78 ± 9.5 years) showed 24% nonunion rate. Age did not predict the development of nonunion.⁶

Additionally, there has been discussion in the recent literature about the stiffness of the plate construction that affects the healing environment and micromotion in the fracture site. A few studies investigated different plate fixation variables as a risk factor for nonunion.^{15,16} The plate material can affect the rigidity of fixation. Stainless steel plates appeared as a risk factor for nonunion compared to titanium plates.^{16,23} There was less callus formed with fractures treated with a stainless steel plate compared with titanium plate.¹⁷ The plate length, the screw selection and the screw placement in the plate can affect the construction rigidity. Constructs with a plate length > 9 holes appeared to fail less likely compared to shorter plates.¹⁵ The plate constructs with all locking screws have been reported to be 2.9 times more likely to develop a nonunion compared to the plate constructs with both locking and nonlocking screws.³⁰ In addition, healed distal femur fractures had more empty plate holes adjacent to fracture site compared to fractures that did not heal.¹⁷ The mini-invasive plate insertion spares the blood circulation to the periosteum. The submuscular plate insertion reduced nonunion rate in distal femur fractures instead of open reduction.^{21,25}

This study explores the predictive value of previously identified explanatory risk factors for a distal femur fracture nonunion and identifies patients who are at risk for distal femur fracture nonunion after lateral locked plating. In a predictive model, there is no need to consider the causality of the individual risk factors which is a common caveat in studies exploring potential risk factors for a given outcome.³¹ This prediction model could be applied into clinical practice to identify and advise patients with known risks before operation and to more carefully follow-up patients with an elevated risk for fracture nonunion.

Our plan is to publish this study in two consecutive articles: the first article examines the patient- and injury- related factors and the second article examines the role of different treatment related factors in the prediction of distal femur fracture nonunion. To avoid selective

reporting and to improve the transparency of the data collection and analysis phases of these two studies, we decided to write this statistical analysis plan before any statistical analyses were conducted. The study results will be reported according to The Transparent Reporting of a multivariable prediction model for Individual Prognosis Or Diagnosis (TRIPOD) -statement.³²

Objectives and hypotheses

The objectives of the first study:

- To determine the rate of secondary surgery due to fracture nonunion of AO/OTA type A and C distal femur fractures treated primarily with lateral locking plate
- To evaluate how accurately the previously identified patient- and injury-related risk factors predict a distal femur fracture nonunion

The objective of the second study:

- To evaluate how accurately the previously identified treatment-related risk factors predict a distal femur fracture nonunion
- To evaluate a secondary prediction model combining the treatment-related risk factors and the three most important patient- and injury-related predictive factors from the first study

STUDY METHODS

This study is a retrospective cohort study conducted in level 1 trauma centre at the Helsinki University Hospital with a catchment population of around one million for these fractures. After receiving permission from our institutional review board, we identified all patients with a distal femur fracture treated at our institution between 2009 and 2018 using the electronic patient record system. Both of our future articles regarding the prediction of distal femur fracture nonunion will use the same patient data.

The detailed inclusion and exclusion criteria are shown in Table 1. We included patients aged 16 years or older with traumatic distal femur fractures. The first surgical procedure had to be performed at our institution in 1 month (≤ 31 days) after trauma. Patients with a stress fracture, a pathological fracture, epicondylar or subchondral fracture, or ligament sprains such as ACL, PCL, MCL or LCL avulsion injuries, were excluded. We included in these studies The AO Foundation/Orthopaedic Trauma Association (AO/OTA) classification 33A- and 33C-type fractures³³ treated with a lateral locking plate. Only distal lateral anatomic locking plates for distal femur were included and any other unconventional plates used in the distal femur were excluded. Those fractures treated with a lateral and medial plate (double plating-method) or with lateral plate and femur nail together were excluded. We excluded patients treated with a retrograde or an antegrade femoral nail, a constrained prosthesis, femoral amputation, non-surgical treatment and patients who died before the final treatment. We excluded the operatively treated unicondylar fractures (AO/OTA classification 33B,) because the fixation methods and principles used for the operative treatment for B-type fractures differ from the A- and C-type fractures.

The first author examined all femur fracture X-rays included in the study. A fracture was classified as a distal femur fracture if a part of the fracture site was located on a metaphyseal

area of distal femur. Metaphyseal area of distal femur was defined with a square-method as proposed by Urs Heim.^{34,35}

We excluded the patients whose follow-up was too short to define the final healing status of the fracture. The patients who had a radiological or clinical union of the fracture site during the follow-up, and the patients who had any surgical intervention to promote the bony union were accepted to this study.

We defined a fracture as nonunited only when a patient had a surgical intervention to promote bony union in the fracture site. In addition, a reoperation done for a plate failure at least 3 months after operation and without a new trauma is assumed in this study to occur because of a nonunion of the fracture.

The radiological union in the x-ray is defined as a bridging callus consolidation on three out of four cortices of fracture site and vanishing of fracture lines during the follow up. If the radiological follow-up ended before the fracture was radiologically united in x-rays, we followed up the patients from electronic patient records of all medical specialties and general medicine at least 12 months after operation and examined their ambulating status and other problems regarding the fracture site. If there were no clinical signs of problems with distal femur fracture such as pain during gait or pain on the fracture site, and those patients did not come back to our institution after 1 year at least, we assumed that the fracture has been healed and those patients were included in the study. Our institution Helsinki university hospital is the only place in our catchment area where distal femur fractures are treated and based on that we assumed that those patients, who had problems with healing such as non-union or plate failure, will return to the Helsinki university hospital for reoperation.

Surgical treatment

The two different plate types used in this study were DePuy Synthes 4,5mm VA-LCP Curved Condylar Plate (Stainless steel) and DePuy Synthes Less invasive stabilization system (LISS) for LCP-DF-plate (Titanium alloy). The fractures included in this study were operated by the senior orthopaedic trauma surgeons or orthopaedic residents. The plate type, screw types and proximal fixation used in the operation were chosen by the treating surgeon. The methods for proximal fixation were 4.5mm locking- and cortical screws and with peri-implantary fractures also cables and 3.5mm proximal locking attachment plates were used. The fracture fixations were performed both with absolute or relative stabilization techniques according to treating surgeon's preference. There were no proper data available from the surgical records if the operation was performed with a mini-invasive or an open technique. There were not any standardized postoperative protocols for weight-bearing or a cast or an orthosis use. Usually, the non-weight-bearing period was 6-10 weeks after operation. After that patients normally continued with half-weight-bearing, and the weight-bearing as tolerated was allowed from the weeks 10 to 12 depending how the fracture was healed. Typically, the follow-up visits were at 6 and 12 weeks at the outpatient clinic and after that if deemed necessary.

Table 1. Inclusion and Exclusion criteria used in the study.

Inclusion

- Age > 16 years- AO/OTA type A or C distal femur fracture- Fracture located on the metaphyseal area of the distal femur (square method)- Operative treatment in the Helsinki University Hospital with a distal femur anatomic lateral locking plate- Operative treatment within 1 month after trauma- Operative treatment between years 2009 and 2018
Exclusion

- Stress fracture- Pathological fracture- An epicondylar or subchondral fracture- A ligament sprain in distal femur- Treatment with a double-plating method or with both plate and nail- Non-surgical treatment and patients who died before the treatment- Treatment with an unconventional plate (other than distal femur plate)- Patients whose follow-up criteria not fulfilled

Data collection

The details of the data used in this study are shown in Table 2.

The principles of the injury-related factors are as follows. Distal femur fractures were classified according to the AO/OTA classification system 2007.³³ High energy trauma was defined as a motor-vehicle accident or a fall from a height of >1m. Low-energy trauma was defined as a fall from a height of < 1m such as a fall from the same level or a fall from a chair or a bed. All fractures were classified as open or closed injuries. Open fracture was defined as a fracture with an open wound or break in the skin near the broken bone. The definition for a periprosthetic fracture in this study was a distal femur fracture above a knee prosthesis. Segmentally comminuted fractures were defined as A3, C2 and C3- fractures according to the AO/OTA-classification. The definition for medial fracture comminution was that more than one fracture line reached the medial cortex on the antero-posterior x-ray forming one or more loose bone fragments on the medial side. Fracture zone length was measured from the postoperative x-rays where the fracture was reduced. The known plate length in millimetres was used to correctly calibrate the x-ray.

The principles of the treatment-related factors are as follows.

1. The x-ray was calibrated using the plate length
2. Plate length in millimetres: Measured as the plate shaft holes first and then in millimetres given from the manufacturer
3. Plate working length: Defined as a distance from the nearest proximal screw to the nearest distal screw on each side of the fracture
4. Empty holes adjacent the fracture site (i.e., on the intact part of the femur)

5. Plate span ratio: defined as a ratio of the plate length to the fracture length
6. Proximal plate length: Defined as number of plate holes proximal to the fracture lines in X-ray
7. Proximal fixation mode: locking screws, locking + cortical screws (hybrid), cortical screws, cables with or without screws
8. Proximal cortices: Defined as the number of proximal cortices fixed with screws or cables above the fracture segment. One cable is defined to correspond to a bicortical screw (i.e., purchase of 2 cortices). The sufficient proximal fixation is defined as a purchase of 8 or more cortices (e.g., minimum of 4 bicortical screws) and a purchase of less than 8 cortices is defined as not sufficient.
9. The number of locking screws in the plate crossing the fracture segment

Table 2. Data set used in the study.
Patient-related factors (Study I)

 - Age at the date of injury - Sex - Body mass index - Diabetes - Smoking
Injury-related factors (Study I)

 - AO/OTA^a classification - Periprosthetic fracture above a knee prosthesis - Open/closed fracture - Trauma energy - Fracture zone length - Segmental comminution (AO/OTA A3, C2, C3) - Medial comminution of the fracture
Treatment-related^b factors (Study II)

 - Plate length in millimetres - Plate working length - Empty holes adjacent the fracture site - Plate span ratio - Proximal plate length - Proximal fixation mode - Proximal cortices - Locking screws in the fracture segment

^a AO/OTA = The AO Foundation/Orthopaedic Trauma Association

^b See text for definition

STATISTICAL PRINCIPLES

Our statistical analysis is based on predictive approach, and we will follow guidelines from Harrell and Heinze et al.^{36,37} We will use logistic regression since our outcome is binary. Our analysis will be three-fold as outlined above. In the first analysis, we will model risk of nonunion using patient- and injury-related variables. In the second analysis, we will use treatment-related variables. The third analysis will be a combined model which include 3–4 most important variables from the first analysis combined with the 3–4 most important from the second model.

Background knowledge based on previous literature was used to form initial set of variables which may be predictive for nonunion. Variable missingness is assessed. We assume Missing Completely at Random (MCAR) for any missing data and multiple imputation is used. Imputation is based on both predictors and outcome variable. Redundancy analysis is then performed to assess any collinearity between predictors and data reduction is performed if reasonable. Binary variables with very high skewness are critically assessed and excluded from final variable set if seen feasible. Model fitting will be done with imputed datasets. For fitted models, overall R² is estimated and used to interpret the applicability of baseline predictors. Variable importance is also assessed using Wald chi-squared test minus degrees of freedom. Calibration plots will be printed for all three models. Multiplicity is not considered since we are not focused in single regression coefficients nor we have specific multiple testing. When appropriate, 95% confidence intervals will be calculated, and associated p-values calculated. Analysis is done with RStudio using rms package.

REFERENCES

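### Plate material, a risk factor the SAP itself cites and which varies in the cohort, is missing from the Study II candidate predictors without a stated reason

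*SAP*

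**What the plan says.** Under Risk factors for non-union, the SAP reports that "Stainless steel plates appeared as a risk factor for nonunion compared to titanium plates", and adds that less callus formed with steel. The opening paragraph of the same section lists plate material among the four factors of a cited predictive algorithm.

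Under Objectives and hypotheses, the first aim of Study II is "To evaluate how accurately the previously identified treatment-related risk factors predict a distal femur fracture nonunion". Statistical Principles says the starting set of variables was drawn from earlier literature.

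Under Surgical treatment: "The two different plate types used in this study were DePuy Synthes 4,5mm VA-LCP Curved Condylar Plate (Stainless steel", the other being the titanium-alloy LISS plate. On selection: "The plate type, screw types and proximal fixation used in the operation were chosen by the treating surgeon". On insertion technique: "There were no proper data available from the surgical records if the operation was performed with a mini-invasive or an open technique".

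The Study II part of Table 2 begins "Plate length in millimetres - Plate working length - Empty holes adjacent the fracture site" and continues with plate span ratio, proximal plate length, proximal fixation mode, proximal cortices and locking screws in the fracture segment. The numbered treatment principles under Data collection cover the same ground. Neither list contains plate type or material.

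Under Statistical Principles, the treatment variables of the combined model are the three or four "most important from the second model".

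**The concern.** The objective covers the treatment factors that earlier studies have linked to nonunion. By the SAP's own account plate material is one of them, and it varies between patients in this cohort. A reader would expect it in the Study II list, or a sentence saying why it is not there.

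Two things follow if the list is applied as it stands. The second model reports on eight factors and is silent on this one. The combined model draws its treatment variables from the same list, so plate material cannot enter it however predictive it might be. The SAP was written before analysis to prevent selective reporting. Adding plate type once results are known would be exactly the unplanned choice it is meant to rule out.

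**Working it through.** The SAP states no sample size, event count or power, so there is no figure of its own to reproduce. The main check is a comparison of its sections.

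**1. Treatment factors linked to nonunion or failure in the background, against Table 2**

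| Factor in the background | In Table 2 (Study II)? | Reason if absent |
|---|---|---|
| Plate length | Yes | – |
| All-locking versus mixed screws | Yes, through proximal fixation mode | – |
| Empty holes near the fracture | Yes | – |
| Mini-invasive versus open insertion | No | Given: no proper data |
| Plate material | No | None |

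Three of the five are covered, one is absent with a reason, and one is absent without. Conversely, plate span ratio, proximal plate length and proximal cortices are listed although the background text reports no nonunion finding for them.

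**2. Surgeon-chosen features, against Table 2**

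Surgical treatment names three: plate type, screw types and proximal fixation. The last two are represented by proximal fixation mode, proximal cortices and locking screws in the fracture segment. Plate type is not represented.

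**3. Is plate type likely to be on record?**

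Both systems are named, plate length in millimetres comes from the manufacturer, and "The known plate length in millimetres was used to correctly calibrate the x-ray". This suggests the implant was identified for each patient. It is an inference, because the SAP does not report completeness for plate type.

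**4. Parameter count**

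Assume linear terms for all numeric items and four categories for proximal fixation mode.
- As written: 7 items × 1 df + (4 − 1) df = 10 df.
- With a binary plate type: 10 + 1 = 11 df.

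**5. Possible size (illustration only)**

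Model: logit(P) = a + 0.75·Z + ln(OR)·M. Here Z is a normal score standing for the other predictors, M is 1 for the higher-risk plate, and a is set to give the overall risk.
- From the SAP: nonunion rates of 6%, 10% and 22%, all quoted in its background.
- Assumed: odds ratio 2, 3 or 4; share on the higher-risk plate 10%, 50% or 90%; latent correlation between M and Z of 0 or 0.5. The C-statistic without plate type is then about 0.68 to 0.75.

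Logistic models with and without M were fitted to 600,000 simulated patients per scenario.

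| Scenario at 10% risk | Gain in Nagelkerke R² for OR 2 / 3 / 4 |
|---|---|
| 50:50 split, correlation 0 | 0.020 / 0.044 / 0.070 |
| 50:50 split, correlation 0.5 | 0.015 / 0.035 / 0.049 |
| 90% on higher-risk plate, correlation 0.5 | 0.003 / 0.006 / 0.008 |

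- At 10% risk, all scenarios: R² gain 0.003 to 0.070, C gain 0.003 to 0.064.
- Over 6% to 22% risk: R² gain 0.002 to 0.094, C gain 0.003 to 0.069.
- At an odds ratio of 1 both gains are zero.

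**The case against.** The strongest reply is that the SAP never promised to model every factor it cites. Literature was used to form a starting set, which leaves room for judgement, and other cited factors such as infection and the medial fracture gap are also absent from Table 2. This does not answer the point. The SAP names infection among the patient- and injury-related factors and discusses the medial gap under fracture comminution, so it presents neither as a treatment factor within the Study II objective. Plate material is one.

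A second reply is that the evidence is contradictory. One paragraph of the background makes titanium the risk and another makes stainless steel the risk, and both cite reference 23. That needs correcting, but both paragraphs treat material as a risk factor, and a prediction model needs no direction in advance.

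A third is that the skewness or redundancy step could remove the term anyway. It could, but those rules screen listed candidates and do not explain why this one was never listed.

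What stands is the objection to the numbers. The odds ratios, plate split and correlation are assumed, and odds ratios below 2 are not in the stated range. With 600,000 simulated patients there is practically no overfitting. In a single-centre cohort with an uncommon outcome, the net gain would be smaller and could be negative. The simulated range therefore cannot carry the conclusion, and it does not need to.

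**Conclusion.** The concern holds. The Study II objective covers plate material, the cohort contains both materials, and the predictor list omits it without a reason. As written, neither the second model nor the combined model can assess it, so the objective is only partly met. This rests on the SAP's text alone and is held with high confidence.

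The effect on predictive accuracy is unknown. It may be negligible if one plate dominates, if the listed predictors already carry the information, or if the association is weak. This should be corrected before analysis; it does not invalidate the models for the factors that are listed.

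**What to change.** Add plate type/material (stainless steel VA-LCP versus titanium LISS) as one binary candidate, both in the numbered treatment factors and in the Study II part of Table 2. Subject it to the same missingness, skewness, redundancy and importance rules as the others. Make it eligible for the combined model without forcing it in. State that the term cannot separate material from plate design, because each material corresponds to one plate system.

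If the omission is deliberate, give the reason and reword the Study II objective so that it covers only the listed factors.

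The cost is one line in the predictor list and one parameter (10 to 11 df under the assumptions above), to be weighed against the number of nonunions. Little or no new data collection is likely if plate type is already recorded, which should be confirmed.

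As a separate minor correction, on which no analysis depends, reconcile the two background statements that give opposite directions for plate material while sharing reference 23.

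### Objective 1's reoperation rate appears to leave out plated patients who die unreoperated before union is established, so it would exceed the proportion of plated fractures actually reoperated

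*SAP*

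**What the plan says.** Under Objectives and hypotheses, the first aim of the first study is "To determine the rate of secondary surgery due to fracture nonunion of AO/OTA type A and C distal femur fractures" that were treated primarily with a lateral locking plate. The target is an operation, counted among plated fractures.

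STUDY METHODS then decides who is in the cohort:

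- **Reoperated patients** qualify by the event itself: "the patients who had any surgical intervention to promote the bony union were accepted to this study". A plate failure also counts as nonunion, because "a reoperation done for a plate failure at least 3 months after operation and without a new trauma is assumed in this study" to result from it. No upper time limit is set.
- **Unreoperated patients** need radiological or clinical union. If x-ray follow-up stopped before union, records are followed for at least 12 months. For patients without symptoms, the rule is that if "those patients did not come back to our institution after 1 year at least, we assumed that the fracture has been healed".
- **Everyone else** is removed: "We excluded the patients whose follow-up was too short to define the final healing status of the fracture". Table 1 repeats this as an exclusion: "Patients whose follow-up criteria not fulfilled".

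The SAP also assumes that patients "who had problems with healing such as non-union or plate failure, will return to the Helsinki university hospital for reoperation". Death is mentioned only as an exclusion before treatment: before the final treatment in the STUDY METHODS text, and simply before treatment in Table 1. STATISTICAL PRINCIPLES describes the logistic models and gives Objective 1 no separate denominator.

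**The concern.** Whether a fracture enters the denominator depends partly on whether the event being counted occurred. Take a patient who is plated, has no x-ray union, is not reoperated and dies in month 4. Healing status is unknown, but the outcome named in Objective 1 is known: there was no secondary surgery. This patient meets neither acceptance condition and drops out. A patient reoperated in month 4 who dies soon afterwards stays in.

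The visit schedule can widen the effect. "Typically, the follow-up visits were at 6 and 12 weeks at the outpatient clinic and after that if deemed necessary". A patient without x-ray union by the last visit has to remain alive, with records, to 12 months to count as healed. The SAP's reference list also includes a cohort study whose title describes high mortality after this fracture. Only the title is available, so no figure is taken from it.

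At stake is the headline descriptive result of the first article. Readers would take it as the share of plated fractures that needed another operation for nonunion.

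**Working it through.** The SAP states no event count, excluded share or mortality, so there is no figure of its own to reproduce. The direction follows from its rules. The size needs assumptions.

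**1. Direction for deaths.** Let N be all eligible plated fractures, R those reoperated for nonunion, and E those excluded, none of them reoperated. Put e = E/N.

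- Reported rate = R/(N-E)
- Proportion of plated fractures reoperated = R/N
- Ratio = 1/(1-e), above 1 whenever E > 0

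For assumed e of 5, 10, 20 and 30% the ratio is 1.05, 1.11, 1.25 and 1.43. A reported 10% would correspond to 9.5, 9.0, 8.0 and 7.0% of all plated fractures, from 10% x (1-e).

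**2. Size under a timing model.** The simulation used 1,000,000 fractures per scenario.

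- From the SAP: reoperation times span 85 to 400 days, the range cited for plate failures in the risk-factor section.
- Assumed: 10% would be reoperated if nobody died; reoperation time triangular with mode 150 days; union time normal, mean 150 and SD 45 days, clipped to 60-365; death Weibull with shape 0.6, scaled to 10, 20 or 30% at one year.
- An unreoperated patient is accepted if union is documented before death or if alive at day 365.

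| Unions documented when they occur | One-year mortality | Excluded | Reported | Actually reoperated | Gap (points) |
|---|---|---|---|---|---|
| All | 10% | 6.1% | 9.88% | 9.28% | 0.6 |
| All | 20% | 12.4% | 9.76% | 8.55% | 1.2 |
| All | 30% | 19.0% | 9.62% | 7.79% | 1.8 |
| 40%, rest at 12 months | 10% | 8.2% | 10.11% | 9.28% | 0.8 |
| 40%, rest at 12 months | 20% | 16.6% | 10.20% | 8.50% | 1.7 |
| 40%, rest at 12 months | 30% | 25.1% | 10.43% | 7.81% | 2.6 |

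The rows agree with step 1: for example, 9.28/(1-0.061) = 9.88.

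A separate, simpler model (constant death hazard, reoperation uniform over 3-12 months, 60% of healers with x-ray union at 3-8 months) gave 10.03, 9.94 and 10.06% reported against 9.35, 8.58 and 7.95% reoperated. The gaps are 0.7, 1.4 and 2.1 points.

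**3. Other baseline risks.** The SAP's background cites nonunion rates of 6% and of 10-22%. Over the same three mortalities the gap is 0.4-1.1 points at 6% and 1.4-4.1 at 22% when all unions are documented as they occur. With 40% documented, the upper ends become 1.6 and 5.7.

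**4. Stopped records.** If a share e is excluded because records end, and a proportion q of them is in fact reoperated, the all-plated rate is (1-e)R' + e q, where R' is the reported rate. With R' = 10% and e = 10%, q of 0, 5, 10 and 20% gives 9.0, 9.5, 10.0 and 11.0%. The reported rate is too high only if q is below R'.

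**The case against.** **The evaluable-only rate is a recognisable quantity.** A patient who dies in the first weeks never had the chance to heal or fail, and the SAP openly restricts itself to fractures whose healing can be determined. At 10% no-death risk the rule returns 9.6-10.4%, close to that risk. This stands as a reason to keep the figure under a clear label. It does not make the figure the rate that Objective 1 words, and the SAP never says that a no-death risk is intended.

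**Clinical union may be accepted earlier.** STUDY METHODS accepts radiological or clinical union during follow-up, and the 12-month rule is spelled out for patients whose x-ray follow-up ended early. If clinical union recorded sooner also counts, exclusions in the 40% setting fall to 6.1, 12.4 and 19.0% and the gaps to 0.6, 1.2 and 1.8 points. This stands: the larger gaps depend on the narrower reading. A gap remains on either.

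**Exclusion of deaths after plating is inferred.** The SAP does not state it, and its text speaks of death before the final treatment. This stands as a caveat. The inference is that such patients meet neither acceptance condition and that no other denominator is given.

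**The size is assumed and may be below sampling error.** With an assumed 200 to 400 fractures, the 95% half-width around 10% is 4.2 to 2.9 points, more than any gap found at that risk. This limits the importance of the point. It does not remove an error of known direction that the plan can avoid cheaply.

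**Conclusion.** The point holds for deaths. On the SAP's acceptance rules as written, plated patients who die unreoperated before union or 12 problem-free months leave the denominator, and the reported rate exceeds the proportion reoperated by the factor 1/(1-e). This rests on two inferences: that these deaths fall under the follow-up exclusion, and that the defined cohort is Objective 1's denominator. The size rests on assumed mortality, timing and documentation of union: about 0.6-1.8 points at 10% no-death risk, and up to 2.6 on the narrower reading of clinical union.

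A reader might infer three stronger things that the SAP does not support:

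- **That every exclusion inflates the rate.** For stopped records this needs a reoperation rate below the reported one. The SAP's assumption that patients return to the same hospital implies this, but does not show it.
- **That the overstatement is as large as 5.7 points.** That is the extreme corner: 22% risk, 30% mortality and 40% of unions seen.
- **That the prediction models are thereby invalid.** A cohort with determinable healing can serve them. The point concerns the descriptive rate only.

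This is a should-fix: a stated result changes in a known direction, at small cost.

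**What to change.** For Objective 1, name all eligible plated fractures as the denominator. Report the cumulative incidence of reoperation for nonunion (Aalen-Johansen), with death as a competing event and censoring at last record. Give it at 12 months and at a later prespecified time. Twelve months alone would drop late reoperations that the outcome definition counts, and the plate failures the SAP cites run to 400 days. In simulation at 10% no-death risk, this estimator at 12 months gave 9.1, 8.5 and 7.7% for 10, 20 and 30% mortality, equal to the actual 12-month proportion. It gave 9.1, 8.4 and 7.7% when 10% of records stopped at random in the first year.

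Keep the evaluable-only rate as a secondary figure, labelled as such. Report exclusions by reason: death, records stop, symptomatic and unoperated, other. The prediction cohort and models stay as planned.

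The cost is SAP wording plus extraction of the dates of reoperation, death and last record, partly from records the plan already reviews. The headline rate becomes somewhat lower. The article will carry two base rates, because the models keep the evaluable-only one, so each needs its label.
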